Statistical Analysis Plan

Effects of mobilization dose in surgical intensive care unit patients on adverse discharge disposition

Original Date: August, 20, 2018

Table of Contents

1. Primary and Secondary Aim Overview.....	2
2. Primary aim.....	2
Hypotheses.....	2
Covariate Data.....	3
Statistical analysis.....	3
3. Secondary aim.....	5
Hypothesis.....	5
Statistical Analysis.....	5
4. Sample Size.....	6
5. Data collection.....	6

1. Primary and Secondary Aim Overview

Primary Aim

The primary aim of this study is to assess the effects of mobilization dose in critically ill patients on adverse discharge disposition (ADD) (primary outcome). The primary hypothesis of this study is that the mobilization dose in the surgical intensive care unit measured by Mobilization Quantification Score (MQS) is associated with ADD.

Secondary Aim

The secondary aim is to evaluate the association between rectus femoris cross sectional area (RFCSA) measured by bedside ultrasound within 48 hours of enrollment and mobilization dose received in the surgical intensive care unit (SICU).

2. Primary Aim

This study aim is driven by the research hypothesis that the MQS - a new method to quantify mobilization dose based on intensity and duration with more granularity than currently used mobilization quantification instruments - reflects the improving effects of early mobilization on discharge disposition.

Exposure variable

The primary exposure variable is the mean daily mobilization dose quantified by the MQS. The MQS is a newly developed score that quantifies mobilization provided by SICU nurses and physical therapists incorporating the mobilization level as well as its duration. The MQS is calculated daily throughout the SICU stay and will be divided by the number of ICU days to arrive at the exposure variable mean daily mobilization dose.

The secondary exposure variable used for comparison is the SICU optimal mobilization score (SOMS).

Primary Outcome

The primary outcome ADD is defined as discharge to facilities providing long-term care assistance for daily activities, including nursing homes and skilled nursing facilities, hospice at the patient's home, hospice in a healthcare facility, or in-hospital mortality.

Hypotheses

Primary Hypothesis

The primary hypothesis is that mobilization dose quantified via MQS predicts adverse discharge disposition.

Secondary Hypothesis

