The key secondary hypothesis is that the MQS predicts ADD better than the SICU optimal mobilization score [SOMS] (Schaller et al., 2016).

We also hypothesize that the MQS predicts ICU length of stay, hospital length of stay, functional independence measure (mmFIM) at ICU and hospital discharge, 3-month mortality, change in muscle mass quantified by change in RF-CSA, ICU coma- and delirium-free days, ICU ventilator-free days, ICU vasopressor-free days, ICU neuromuscular blocking agent free days, opioid dosage, corticosteroid days, and physical work capacity 3 months after hospital discharge quantified by the Duke Activity Status Index (DASI).

Covariate Data

Predefined confounders in multivariable adjusted analyses include APACHE2 (Knaus, Draper, Wagner, & Zimmerman, 1985), sex-adjusted rectus femoris cross sectional area (RFCSA) (Janssen, Heymsfield, Wang, & Ross, 2000) measured via bedside ultrasound upon admission, and the Risk Quantification Index for 30-day Postoperative Morbidity (PSS morbidity) (Dalton et al., 2011).

RFCSA measured by bedside ultrasound has been shown to be an independent predictor of adverse patient outcomes (Mueller, Eikermann 2016).

RFCSA will be adjusted for sex using published skeletal muscle mass values of the lower body of healthy adults (Janssen et al., 2000). Thus, RFCSA of female patients are multiplied with the coefficient 1.484, whereas male patients represent the reference group (adjustment coefficient 1). Sex-adjusted RFCSA will be used for further statistical analyses.

Statistical Analysis

All analyses are performed prospectively with prespecified endpoints and statistical methods.

Primary analysis

Unadjusted Analysis: We will conduct univariate logistic regression analysis to investigate the association between mobilization dose quantified by MQS and ADD.

Adjusted analysis: Multivariable logistic regression (mean daily mobilization dose (MQS)/ ADD) analyzing whether mobilization dose predicts adverse discharge independent from the defined covariates (APACHE2, PSS Morbidity score, and sex adjusted admission RFCSA).

Secondary analyses

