We will perform Net Reclassification Index and c-statistics to compare the predictive capability for ADD of the MQS to the SOMS. To further confirm the robustness of our results we will conduct Aikaike Information Criterion (AIC) and likelihood ratio test. AIC provides the relative quality of the estimated model. The likelihood ratio test compares the goodness of fit of two statistical models.

Multivariable logistic regression will be performed to evaluate the relationship between mean daily mobilization dose and other binary secondary outcomes controlling for above defined covariates. Zero truncated negative binomial regression will be used to analyze the association between mobilization dose and the secondary outcomes ICU and hospital length of stay. Negative binomial regression will be used to analyze the association between mobilization and the secondary outcomes coma- and delirium-free days, NMBA-free days, ventilator-free days, and functional independence measure (mmFIM) at ICU and Hospital discharge.

We will use linear regression to analyze the association between mobilization and physical work capacity 3 months after hospital discharge quantified by the Duke Activity Status Index (DASI) and opioids dosage (mg), if normality assumption is satisfied. Otherwise, transformation of the variables will be performed, and the transformed variables will be used as the outcome in the linear model.

Planned Sensitivity Analyses

Evaluation of confounder model: AUC-Analysis including the predefined confounders to determine the Area Under the receiver operator curve.

Categorized exposure variable: (2-quantile [high, low mobilization dose], tertiles [low, intermediate, high mobilization dose])

Alternative Exposure Variable: For each patient, mobilization data will be centered, and we will perform simple linear regression with the individual mean mobilization dose being the estimated intercept of each patient. The estimated slope from the linear regression will be considered as the change rate of mobilization dose. Two exposures will be included in our model, the slope of the mobilization dose and the intercept. We will conduct multivariable logistic analysis controlling for the same confounder variables (expected 4DoF: Intercept, Slope, APACHE2, RFCSA (continuous), PSS morbidity) from the primary analysis.

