Evaluate the AUC with alternative Exposure Variable (intercept/ slope): We will compare discriminative ability of our primary model to a model with two exposure variables (intercept (mean mobilization dose for each patient) and slope) utilizing Net Reclassification Index, Brier Score and c-statistics.

Generalized propensity score: In an exploratory approach, accounting for the degrees of freedom available, we will include a generalized propensity score to reduce bias induced by discrepancies in patient characteristics. The propensity score will be generated from different covariates identified as influencing the exposure including APACHE, GCS at enrollment, ASA at admission, PSS-Morbidity, duration of ventilation, duration of sedation, duration of delirium, opioid dose, vasopressors. The propensity score will be confined for a binary exposure variable. To derive at a binary variable, we will categorize the mean mobilization dose (MQS) into two categories, high vs. low.

Subgroup analyses: We will perform a subgroup analysis in patients who received surgery upon admission to the ICU.

Planned Exploratory Analyses

We aim to explore the association of other variables that can be used to quantify mobilization intensity and duration (other than the composite exposure MQS) and adverse discharge disposition.

The additional variables used to quantify mobilization intensity and/or dose are:

- Mean highest achieved level of mobilization therapy (Daily highest achieved ICU mobilization scale level/ICU days)
- Highest achieved mobilization level using ICU mobilization score
- Mean number of daily mobilization sessions (Total number of mobilization units/ICU days)
- Mean duration of mobilization units according to MQS (Total duration of mobilization treatment based on MQS/number of sessions throughout the ICU stay)
- Fraction of days mobilized (Number of mobilization days/ ICU days)
- Early mobilization frequency (Total number of mobilization units from day 1 through 3 on the ICU)

We will use multivariable logistic regression for exploratory analyses analyzing the association between the above-mentioned variables used to quantify mobilization intensity and/or dose.

3. Secondary Aim

Exposure variable

The RFCSA assessed through bedside ultrasound measurements within 48h is used as a continuous exposure variable.

Outcomes

The outcome for the secondary aim of the study is the repeatedly measured daily mobilization dose as quantified by the MQS.

Hypothesis

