On ICU admission, patients' baseline characteristics [age, sex, race, ethnicity, height, weight, admission diagnoses, Charlson comorbidity index (CCI), ASA PS, Frailty Score, Short Nutritional Assessment Score Questionnaire (SNAQ) Score reason for ICU admission] will be noted. Admission laboratory data and vital signs to calculate the APACHE II score, will be recorded as well as the severity of organ dysfunction [Sequential Organ Failure Assessment (SOFA) score]. SOFA scores will be obtained within 48 hours of SICU admission and on days when follow up ultrasound measurements are conducted (every 8 days/ at ICU discharge). Daily laboratory data, vital signs, medication and ventilation/ABG will be noted. We will further collect data at ICU discharge, Hospital discharge and 3 months after discharge. A summary of the data that we will collect is listed below.

Baseline

Medical Record Number, First name, Last name , Date of Birth, Age, Sex, Race, Ethnicity, Height, Weight at ICU admission, ICU admission [date] , Hospital admission [date], Admission category, Patient had surgery prior to inclusion (y/n) Date of surgery, Surgery CPT Code, Charlson Comorbidity Index, ASA, Frailty Phenotype Modified, Short Nutritional Assessment Questionnaire, APACHE II, Barthel Index 2 weeks prior to admission, Glasgow Coma Scale motor component at enrollment, Absence of lower extremity (y/n), Pregnancy (y/n), Procedural Severity Score.

Follow-up

Richmond Agitation and Sedation Score (RASS), SOFA score, Medical Research Council Muscle scale (MRC scale), Confusion Assessment Method for the ICU (CAM-ICU), Nutrition, Renal replacement therapy (y/n)

Mobility

MQS score, SOMS score, Physical Therapy (PT) time [mins], nonPTMobilization [mins], walking distance [feet], Rectus femoris diameter left [cm²], Rectus femoris diameter right [cm²]

Vital Signs

Systolic blood pressure, diastolic blood pressure, mean arterial blood pressure (MAP), Respiratory rate, Body temperature, Heart rate.

Laboratory

Hb [g/dL], Hk, Creatinine [mg/dL], Urine output [μ mol/L], Alb (g/dL), INR, blood Glucose [mg/dL], serum sodium (Na) [mEq], K [mEq/L], glomerular filtration rate (GFR), Bilirubin [μ mol/L], CRP, WBC count, CKD, Platelets [$\times 10^9/L$].

Medication

Sedation needed (y/n), Steroids (y/n), Opioids total dose per day [morphine equivalent dose, mg], Vasopressors (y/n), NMBAs (y/n + drug), Propofol (y/n), Total propofol dose per day.

Ventilation/ABG

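### Ventilation, vasopressors, opioid dose and delirium are treated both as outcomes of whole-stay MQS and as influences on it, so 'MQS predicts' cannot be interpreted for these endpoints

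*SAP*

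**What the plan says.** Section 2, Exposure variable, sets the window: "The MQS is calculated daily throughout the SICU stay and will be divided by the number of ICU days". The Secondary Hypothesis then names as quantities that the MQS predicts "ICU ventilator-free days, ICU vasopressor-free days, ICU neuromuscular blocking agent free days, opioid dosage, corticosteroid days", together with coma- and delirium-free days.

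Under Secondary analyses, a negative binomial model is given for the "secondary outcomes coma- and delirium-free days, NMBA-free days, ventilator-free days", and linear regression for "opioids dosage (mg), if normality assumption is satisfied". No model is named for vasopressor-free or corticosteroid days. The predefined confounders are APACHE2, PSS morbidity and sex-adjusted admission RFCSA.

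Under Planned Sensitivity Analyses, the direction is the other way round: "The propensity score will be generated from different covariates identified as influencing the exposure", and the list includes "duration of ventilation, duration of sedation, duration of delirium, opioid dose, vasopressors".

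**The concern.** A day on which a patient is ventilated, delirious, on vasopressors or heavily dosed with opioids may be a day with less mobilization because of that state. Such a day lowers the mean MQS and at the same time worsens the outcome. An association then appears whether or not mobilization changes anything, and the SAP itself says that these variables act on the exposure.

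Nothing in the plan separates the two directions. Exposure and outcome share one window, and no lag, landmark or time-varying model is given for these endpoints. The covariates describe the patient at admission or the procedure, not the course in the ICU. The propensity score cannot help either, because ventilation duration cannot be a covariate in a model where ventilation is the outcome. At stake is whether a significant result for these secondary hypotheses means anything beyond the fact that sicker days are less mobile days.

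**Working it through.** **1. The statements side by side**

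| Quantity | As outcome (Secondary Hypothesis) | As influence on MQS (Generalized propensity score) | Model named (Secondary analyses) |
|---|---|---|---|
| Ventilation | ventilator-free days | duration of ventilation | negative binomial |
| Delirium | coma- and delirium-free days | duration of delirium | negative binomial |
| Opioids | opioid dosage | opioid dose | linear |
| Vasopressors | vasopressor-free days | vasopressors | none |
| NMBA | NMBA-free days | not listed | negative binomial |
| Corticosteroids | corticosteroid days | not listed | none |

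The dual role is documented for the first four rows only.

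**2. The plan's own figure.** Sample Size and Power gives r = 0.25, N = 150 and alpha 0.05 (two-sided assumed). Power = Φ(atanh(r)·√(N−3) − 1.960) = Φ(0.2554 × 12.124 − 1.960) = Φ(1.137) = 0.872. The stated power above 0.8 is reproduced. Only N and alpha are carried forward.

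**3. Chance of a favourable significant result with no effect of MQS.** Let ρ be the size of the partial correlation created by the reverse path alone. The SAP gives no value, so ρ is an assumption. With three covariates the chance is Φ(atanh(ρ)·√(150−3−3) − 1.960), and √144 = 12. For ρ = 0.20: Φ(0.2027 × 12 − 1.960) = Φ(0.473) = 0.682.

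| ρ (assumed) | 0.05 | 0.10 | 0.15 | 0.20 | 0.25 | 0.30 | 0.40 |
|---|---|---|---|---|---|---|---|
| Chance | 0.087 | 0.225 | 0.442 | 0.682 | 0.865 | 0.960 | 0.999 |

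The nominal chance in that direction is 0.025. A chance of 0.95 needs ρ = tanh((1.960 + 1.645)/12) ≈ 0.29; a chance of 0.99 needs about 0.34.

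**4. Dependence on the outcome definition.** Simulation of 1,000 data sets of 150 patients per setting, with no effect of MQS. All inputs are assumptions: ICU stay of 2 days plus a negative binomial count with mean about 6; log-odds of a treated day −0.5 + 0.5 × severity + a standard normal term; mean daily MQS 6 on untreated days, between-patient SD 3, day-to-day SD 4. The models are linear (on a log scale for the two in-ICU counts) and adjusted for baseline severity, a simplification of the planned negative binomial. Entries are the share of data sets with a significant favourable result. Ranges run over how strongly long stays go with more treatment.

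| MQS on treated days relative to other days | Share of ICU days treated | Days treated | 28-day free days | Free days inside the ICU stay |
|---|---|---|---|---|
| 100% | 2% | 2.5% | 1-2% | 2-3% |
| 75% | 31% | 17-20% | 10-12% | 5-14% |
| 50% | 79% | 53-63% | 35-41% | 8-42% |
| 25% | 98% | 88-93% | 69-75% | 12-75% |

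The rate returns to nominal when treatment does not lower MQS, so the reverse path drives the excess. For free days counted inside the ICU stay, the rate is lowest when longer stays go with more treatment.

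**5. What a landmark achieves.** Here treatment status was simulated as persisting from day to day, with no effect of MQS, against a two-sided nominal 5%. The whole-stay analysis rejected in 100% of data sets. MQS on days 1-3 against the outcome from day 4 still rejected in 74-99%. Adding adjustment for treatment on days 1-3 brought this to about 2-9%. When unmeasured severity was allowed to drive both MQS and later treatment, the adjusted landmark rejected in 8-71%, depending on the assumed strength.

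**The case against.** The SAP speaks of prediction and association for these endpoints and claims no benefit. Its wording about effects concerns ADD, and a whole-stay association is a legitimate descriptive aim for a new score. These are also a few among many secondary outcomes. All of this stands, and it limits the point to how the results may be read. It does not remove the point: prediction also needs the predictor to come before the outcome, and here it does not.

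A reader might infer that a spurious benefit is near certain. The documents do not support that. They do not say how far MQS falls on treated days, how common treatment is, how MQS is scored, or over what window free days are counted. The rate runs from near nominal to near 100% over plausible settings.

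A reader might also extend the contradiction to every treatment endpoint. NMBA and corticosteroids are not on the SAP's list of influences. For NMBA a mechanism is plausible; for corticosteroids only the common window is documented.

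**Conclusion.** The point holds for four endpoints: ventilator-free days, vasopressor-free days, opioid dosage, and coma- and delirium-free days. For these the SAP states both directions, and the analysis as planned cannot tell them apart. Significant associations can arise well above the nominal rate with no effect of mobilization. How far above rests on two things that the SAP does not give: the fall in MQS on treated days and the free-day definition. No single percentage should be attached to it. NMBA-free days deserve the same caution on grounds of mechanism, and corticosteroid days on grounds of the window alone.

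The covariate sentence under Secondary analyses is attached to the binary outcomes. Assuming adjustment in the count and linear models as well is the reading more favourable to the plan, and the problem remains under it.

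**What to change.** In the Secondary Hypothesis and Secondary analyses, describe the whole-stay regressions for these endpoints as descriptive co-occurrence of mobilization and treatment or state, in place of prediction by the MQS. State the window over which free days are counted.

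Add a supportive landmark analysis. The exposure is mean MQS on ICU days 1-3. The outcome is the treatment or state per ICU day from day 4 on (for opioids, mean daily morphine equivalents). Adjust for the same treatment or state on days 1-3, including status on day 3, and for the predefined covariates. The SAP already uses days 1-3 for early mobilization frequency, though for session counts against ADD.

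The cost is SAP wording and some programming. MQS, medication and ventilation data are recorded daily according to the SAP. It lists CAM-ICU and RASS without a frequency, so the delirium version depends on their schedule. Patients who leave the ICU or die before day 4 drop out of the supportive models, and intervals widen. Confounding by severity remains, so the landmark result should not be read as a causal effect either.

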Primary hypothesis

The primary hypothesis is that RFCSA is an independent predictor of mobilization dose in the SICU.

Statistical Analysis

All analyses are performed prospectively with prespecified endpoints and statistical methods.

We will conduct a generalized linear mixed effect model to analyze whether the RFCSA quantified via bedside ultrasound is an independent predictor of daily mobilization dose in the ICU.

Predefined confounders include the Barthel Index at hospital admission, APACHE2 and Charlson Comorbidity Index (CCI).

Secondary analysis

We will conduct a generalized linear mixed effect model to analyze whether the RFCSA quantified via bedside ultrasound is an independent predictor of daily mobilization dose in the ICU utilizing an alternative exposure variable. The exposure variable will be the binary variable "Sarcopenia

yes/no". Sarcopenia is quantified by RFCSA assessed through bedside ultrasound measurements within 48h. We will apply Youden's Index to define the optimal cutoff point of RFCSA for Sarcopenia. (Mueller, Eikermann 2016).

Sarcopenia is a clinical syndrome that describes progressive and generalized loss of skeletal muscle mass and strength and is associated with patient outcomes. (Delmonico, Harris, Lee, J Am Geriatr Soc, 2007)

Sample Size and Power

Based on data obtained by the same centers in the SOMS trial (Schaller et al., 2016) there is a correlation between mobilization dose and discharge disposition of 0.25. We therefore calculate that a sample size of 150 patients provides a power of >0.8 to identify a significant effect (alpha-error: 0.05) for our primary outcome.

Data collection

Data collection

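### Sex enters the analyses only through a fixed 1.484 multiplier on female RFCSA; no model has a sex term, so the secondary-aim RFCSA effect would be biased if that constant is materially off and sex is related to mobilization dose

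*SAP*

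**What the plan says.** In SAP section 2 (Primary Aim, Covariate Data) the adjustment is made "using published skeletal muscle mass values of the lower body of healthy adults". The rule is that "RFCSA of female patients are multiplied with the coefficient 1.484, whereas male patients represent the reference group", and the section ends with "Sex-adjusted RFCSA will be used for further statistical analyses".

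The covariates of each model are:

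- **Adjusted primary model (section 2, Primary analysis):** MQS must predict ADD "independent from the defined covariates (APACHE2, PSS Morbidity score, and sex adjusted admission RFCSA".
- **Secondary-aim mixed model (section 3, Statistical Analysis):** "Predefined confounders include the Barthel Index at hospital admission, APACHE2 and Charlson Comorbidity Index (CCI".
- **Exploratory propensity score (section 2, Planned Sensitivity Analyses):** covariates "including APACHE, GCS at enrollment, ASA at admission, PSS-Morbidity, duration of ventilation, duration of sedation, duration of delirium, opioid dose, vasopressors".

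None of the three lists contains sex. No planned sensitivity analysis varies the constant or stratifies by sex. Sex is recorded at baseline (Data collection).

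In the secondary aim RFCSA is the exposure: "The RFCSA assessed through bedside ultrasound measurements within 48h is used as a continuous exposure variable". That section does not repeat that the value is sex-adjusted. The sarcopenia analysis that follows sets a single Youden cutoff on RFCSA, also without mentioning sex.

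**The concern.** Muscle mass is roughly area times length. A male/female mass ratio therefore equals the area ratio only if muscle length is the same in both sexes. If the true area ratio in these patients is below 1.484, women's values are over-corrected, and sex-adjusted RFCSA partly encodes being female. If it is above 1.484, they are under-corrected and the reverse holds. Without a sex term, the model attributes to RFCSA whatever relation sex has with mobilization dose.

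This matters most in the secondary aim, whose hypothesis is that RFCSA is an independent predictor of dose. A leftover sex difference can then weaken a real association or create a spurious one. In the primary model RFCSA is only a covariate, so less is at stake for the MQS odds ratio.

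**Working it through.** **The plan's own figures.** The value 1.484 cannot be re-derived, because the SAP does not give the source values. The only stated power (above 0.8 with 150 patients and a correlation of 0.25) concerns the primary outcome. It reproduces two-sided: atanh(0.25) × √147 − 1.96 = 0.2554 × 12.124 − 1.96 = 1.137, and Φ(1.137) = 0.872. The present point does not affect it.

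**How far an area ratio could lie from 1.484.** Area ratio = mass ratio × (female/male muscle length). Assumed length ratios of 0.95, 0.93 and 0.90 give 1.41, 1.38 and 1.34. Isometric scaling gives 1.484^(2/3) = 1.30. These are illustrations, not estimates for this population.

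**Assumptions for the secondary aim** (none is in the SAP except n = 150 and the 1.484):

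- 45% women
- relative muscle with the same distribution in both sexes, CV 30%
- true slope 0.25 per SD
- direct effect *g* of female sex on dose of −0.4, 0 or +0.4 SD
- true area ratio *k* from 1.2 to 1.6
- a simple linear model of one dose value per patient in place of the mixed model with its covariates

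**Formulae.** Let c = 1.484/k and D = (c − 1)/0.30, with 0.45 × 0.55 = 0.2475.

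- W = 0.55 + 0.45c²; B = 0.2475D²; S = 0.25(0.55 + 0.45c)
- Slope without sex = (S + 0.2475·D·g)/(W + B)
- Slope with sex = S/W

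**Example, k = 1.3.** c = 1.142, D = 0.472, W = 1.136, B = 0.055, S = 0.266, and 0.2475D = 0.117.

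- g = −0.4: (0.266 − 0.047)/1.191 = 0.184
- g = 0: 0.266/1.191 = 0.223
- g = +0.4: (0.266 + 0.047)/1.191 = 0.262
- With a sex term: 0.266/1.136 = 0.234, whatever *g* is

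| True ratio k | c | g = −0.4 | g = 0 | g = +0.4 | With sex term |
|---|---|---|---|---|---|
| 1.2 | 1.237 | 0.14 | 0.20 | 0.25 | 0.22 |
| 1.3 | 1.142 | 0.18 | 0.22 | 0.26 | 0.23 |
| 1.4 | 1.060 | 0.22 | 0.24 | 0.26 | 0.24 |
| 1.484 | 1.000 | 0.25 | 0.25 | 0.25 | 0.25 |
| 1.6 | 0.928 | 0.28 | 0.25 | 0.23 | 0.26 |

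**Power and type I error** by simulation of the same model at n = 150, without a sex term (accurate to a few percentage points):

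| True ratio k | Power, g = −0.4 | Power, g = 0 | Power, g = +0.4 | Type I error, g = ±0.4 |
|---|---|---|---|---|
| 1.2 | 0.53 | 0.84 | 0.96 | about 10% |
| 1.3 | 0.67 | 0.86 | 0.95 | about 8% |
| 1.4 | 0.78 | 0.88 | 0.90 | about 5% |

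With g = 0, type I error is 5% at every ratio. With a sex term, power is about 0.86 to 0.87 and type I error about 5% throughout. The higher power at g = +0.4 is no gain, because the false-positive rate rises with it.

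**Primary model.** A large-sample simulation used 40% women, a true MQS odds ratio of 0.607 per SD and true ratios from 1.2 to 1.6.

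- With no direct sex effect, the odds ratio without a sex term is 0.60 to 0.61 whatever the ratio.
- If sex shifts dose by ±0.3 SD and the log-odds of ADD by 0.5, it is 0.57 to 0.64 without a sex term and 0.60 to 0.61 with one.
- At exactly 1.484 it still runs from 0.59 to 0.64 in that case, so this part comes from omitting sex and not from the constant.

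**If the secondary aim means unadjusted RFCSA.** With a true ratio of 1.484, direct sex effects of ±0.3 SD and 40% or 50% women, the slope runs from 0.13 to 0.28. With a sex term it is 0.28 to 0.29 on the same scale.

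**The case against.** The multiplier is prespecified, has a cited source, and is a legitimate way to put both sexes on one scale. The SAP contains no contradiction or arithmetic error here. It also gives no RFCSA sex ratio and nothing to suggest that women are mobilized less or more than men. The size of the problem rests on assumed values, and the calculation replaces a mixed model of repeated daily doses with one value per patient. All of this stands, so the figures show sensitivity and do not predict this trial's result.

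A reader might infer three stronger points, none of which the SAP supports:

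- **That any error in the constant distorts the result.** At a true ratio of 1.4 with no direct sex effect, the slope is 0.24 against 0.25 and type I error is nominal. Scale error and a direct sex effect can also offset each other: at 1.2 with g = +0.4 the slope is 0.25.
- **That the plan necessarily loses power.** It does so in the table only if women's dose is lower. The loss nearly vanishes with no sex effect, and apparent power rises if their dose is higher.
- **That the primary result is confounded by the multiplier.** The odds ratio moves visibly only if sex relates to both dose and ADD, and then it does so even with an exact constant.

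What remains is that the plan fixes a quantity the data could estimate, and that section 3 does not name the version of RFCSA it uses.

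**Conclusion.** The concern holds in conditional form and is minor. Bias in the secondary-aim coefficient that matters for inference needs two things together: a true area ratio materially different from 1.484, and a relation of sex to dose. A wrong ratio alone mainly attenuates or rescales the slope, to 0.20 at a ratio of 1.2 and 0.22 at 1.3.

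With both present and a sex effect of 0.4 SD, the slope ranges from 0.14 to 0.26 for ratios of 1.2 to 1.4. At 1.6 the direction of the bias reverses (0.28 or 0.23), and at 1.484 there is none. The sign cannot be known beforehand, which is the main argument for letting the data settle it. That the constant is wrong is a possibility raised by the step from mass to area; the SAP does not establish it. For the primary MQS odds ratio a sensitivity check is enough.

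**What to change.** 1. Section 3, Statistical Analysis: add sex as a covariate to the mixed model, keeping the prespecified 1.484.
2. Section 3, Exposure variable: state that the exposure is the sex-adjusted RFCSA defined in section 2, and that the sarcopenia cutoff is applied to the same quantity.
3. Section 2, Planned Sensitivity Analyses: add a version of the adjusted primary model with sex as a further covariate.

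The cost is one degree of freedom per model and no new data, since sex is already recorded. If 1.484 is right, almost nothing is lost. If it is wrong, a small scale error in the women's values remains (slopes of 0.22 to 0.26 against 0.25 in the scenarios above). Raw RFCSA plus sex would avoid the constant, but it puts the coefficient on the raw-area scale, so it is better as a supplement than as a replacement.

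### The adjusted model for mobilization dose (MQS) and adverse discharge (ADD) omits the Barthel Index and CCI, which the SAP collects and uses as confounders when dose is the outcome; one added sensitivity model would close the gap

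*SAP*

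**What the plan says.** SAP section 2 (Statistical Analysis, Primary analysis) sets an adjusted logistic model of ADD on mean daily MQS. It tests whether dose predicts ADD "independent from the defined covariates (APACHE2, PSS Morbidity score, and sex adjusted admission RFCSA". The intercept/slope sensitivity model reuses these confounders. The categorized-exposure, subgroup and exploratory analyses name no others.

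The one analysis with a wider covariate set is the propensity score under Planned Sensitivity Analyses: "In an exploratory approach, accounting for the degrees of freedom available, we will include a generalized propensity score". It draws on "covariates identified as influencing the exposure including APACHE, GCS at enrollment, ASA at admission, PSS-Morbidity" and several variables from the ICU stay. The list is open-ended, but neither the Barthel Index nor CCI is on it, and MQS is split into high and low.

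In section 3, daily MQS is the outcome and rectus femoris cross-sectional area (RFCSA) the exposure. The hypothesis reads "The primary hypothesis is that RFCSA is an independent predictor of mobilization dose in the SICU", and the adjustment set is "Predefined confounders include the Barthel Index at hospital admission, APACHE2 and Charlson Comorbidity Index (CCI".

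Both variables are in the Baseline list under Data collection: "APACHE II, Barthel Index 2 weeks prior to admission" and "Surgery CPT Code, Charlson Comorbidity Index, ASA, Frailty Phenotype Modified".

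**The concern.** Mobilization dose is care that patients received, not care assigned to them. The adjusted model therefore carries the claim that MQS predicts ADD independently of how ill or limited the patient already was.

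In section 3, RFCSA is the exposure and APACHE2 a covariate. Naming Barthel and CCI as confounders there treats them as related to mobilization dose beyond RFCSA and APACHE2, which are two of the three ADD covariates. ADD covers discharge to long-term care for daily activities, hospice, or death in hospital, so a link with prior function and comorbidity is plausible.

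If patients with poorer function or more disease are mobilized less and also have more ADD, the omitted part makes MQS look protective, which is the direction the study hopes to find. As written, no named analysis would show whether the result survives adjustment for these two variables.

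**Working it through.** **1. The plan's own figure.** Inputs from Sample Size and Power: n = 150, alpha 0.05 (taken as two-sided), and the statement that "there is a correlation between mobilization dose and discharge disposition of 0.25". Fisher z power is Phi(atanh(r)·sqrt(n−3) − 1.96). With atanh(0.25) = 0.2554 and sqrt(147) = 12.12, this is Phi(3.097 − 1.96) = 0.872. The stated power above 0.8 is reproduced.

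**2. The covariate sets side by side.**

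| Analysis | Outcome | Covariates named |
|---|---|---|
| Adjusted primary model | ADD | APACHE2, PSS morbidity, sex-adjusted RFCSA |
| Intercept/slope model | ADD | the same three |
| Propensity score (exploratory) | ADD | nine items, neither Barthel nor CCI |
| Secondary aim | daily MQS | Barthel, APACHE2, CCI (RFCSA is the exposure) |

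The SAP gives no reason for the difference.

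**3. Possible size of the bias (all inputs assumed).** The SAP gives no association of Barthel or CCI with MQS or ADD, and no ADD rate. Suppose MQS has no effect, and one omitted factor has correlation of size a with both MQS and ADD, in opposite directions. Let the planned covariates explain a share c² of that factor. The spurious partial correlation is then, in size,

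r = a²(1 − c²) / (1 − a²c²),

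and with three covariates the shift is d = atanh(r)·sqrt(150 − 3 − 3) = 12·atanh(r). The false-positive rate is Phi(d − 1.96) + Phi(−d − 1.96). For a = 0.25 and c² = 0.25: r = 0.0469/0.9844 = 0.0476, d = 0.572, rate 8.8%.

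| a | c² = 0 | c² = 0.25 | c² = 0.50 |
|---|---|---|---|
| 0.10 | 5.2% | 5.1% | 5.0% |
| 0.15 | 5.8% | 5.5% | 5.2% |
| 0.20 | 7.7% | 6.5% | 5.7% |
| 0.25 | 11.7% | 8.8% | 6.7% |
| 0.30 | 19.1% | 13.2% | 8.7% |

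Simulated logistic models (n = 150, ADD 30 to 40%; 30% only for a = 0.10 and 0.15) agree to within one or two percentage points. The spurious odds ratio per SD of MQS is 0.95 to 0.98 at a = 0.10 to 0.15. With 25 to 50% overlap it is 0.93 to 0.96 at a = 0.20, 0.89 to 0.93 at a = 0.25, and 0.85 to 0.90 at a = 0.30. With the factor in the model, the false-positive rate returns to about 5%.

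**4. Cost of two more terms.** The model goes from four terms to six. At an assumed 30% ADD there are 45 events: 45/4 = 11.3 and 45/6 = 7.5 per term. At 20% (30 events) it is 7.5 and 5.0; at 50% (75 events) 18.8 and 12.5.

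Fisher z power at an adjusted r of 0.25 is Phi(0.2554·sqrt((147 − k)(1 − R²)) − 1.96), where k is the number of covariates and R² the further share of MQS variance that the two variables explain:
- k = 3, R² = 0: 0.865
- k = 5, R² = 0: 0.861
- k = 5, R² = 0.04 / 0.09 / 0.16: 0.847 / 0.827 / 0.797

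Power falls below 0.8 once R² exceeds about 0.15.

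**The case against.** A reader might infer that the SAP contradicts itself, or that it concedes Barthel and CCI confound the primary comparison. It does neither. Section 3 concerns RFCSA and MQS, and a confounder there need not be related to ADD. Nothing in the SAP says that either variable predicts ADD; that step rests on clinical plausibility.

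The three planned covariates are also defensible. They cover acute severity, procedural risk and admission muscle, and the SAP describes RFCSA as a predictor of outcome in its own right. Prior reserve is thus partly represented. The SAP's attention to degrees of freedom may explain a short list, though it does not say so. The propensity score is open-ended and includes ASA, so it may cover part of the gap.

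A reader might also take the 19% cell as the expected error rate. It needs a factor tied to both MQS and ADD more strongly than the SAP's own correlation of 0.25 between dose and disposition, and not captured at all by the three covariates. At a = 0.10 the rate is nominal.

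Nor is the Barthel wording clearly an error. Section 3 places the index at hospital admission and the Baseline list two weeks before it, but both could describe one score taken at admission about earlier function.

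These points lower the severity. They do not remove the gap: the adjusted primary model lists a closed set, and an exploratory analysis of dichotomized MQS that names neither variable does not replace baseline adjustment of the continuous exposure.

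**Conclusion.** The point stands as a cheap improvement of low to moderate severity. The SAP uses Barthel and CCI as confounders when dose is the outcome, collects both, and names neither in any analysis of MQS and ADD.

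The direction of bias, towards a protective MQS, assumes that poorer function or more comorbidity means less mobilization and more ADD after the planned adjustment. The size cannot be derived from the SAP. Under the assumed correlations of 0.1 to 0.25 with 25 to 50% overlap, the false-positive rate is about 5 to 10%; higher rates need stronger and less shared confounding. The documents do not support saying that the planned primary analysis is invalid or that its result would be spurious.

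**What to change.** - Keep the three-covariate model as the primary adjusted analysis.
- Prespecify one sensitivity logistic model for ADD with MQS, APACHE2, PSS morbidity, sex-adjusted RFCSA, baseline Barthel Index and CCI. Report its MQS odds ratio and 95% CI beside the primary one.
- If there are fewer than 60 ADD events (10 per term for six terms), fit both models with Firth penalized likelihood for this comparison, so that the estimator is the same.
- Do not make the primary claim depend on an undefined agreement between the models. If the MQS association is materially attenuated, or its CI includes 1 in the six-term model, report that independence from prior function and comorbidity is not shown. Note alongside that odds ratios are non-collapsible, so some shift can occur without confounding, and that the larger model is less precise.
- Reconcile the Barthel reference time between section 3 and the Baseline list.

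The cost is SAP wording and one extra model; no new data are needed. The downside is confined to the sensitivity model: fewer events per term and some loss of precision, small unless the two variables explain much of the variance of MQS.
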